6.5.6. Physical Examination

Physical examination findings will only be listed.

6.5.7. Left Ventricular Ejection Fraction (LVEF)

LVEF% will be summarized as frequency (number and percentage) of patients with:

- A shift from baseline normal to at least one result below the institutional lower limit of normal during the on-treatment period;
- ≥ 20 -point decrease from baseline in LVEF%.

A patient will be included in the categories above if any post-baseline assessment (including unscheduled assessments) meet the criteria; however only post-baseline assessments which use the same method of assessment (ECHO or MUGA) as baseline will be considered.

6.5.8. Performance Status

The ECOG shift from baseline to the highest score during the post-baseline period will be summarized by Cohort.

6.5.9. Mood and Suicidal Ideation and Behavior Analyses

- **The Beck Depression Inventory-II (BDI-II) - Assessment of Mood**

An assessment of mood will be administered to patients via the Beck Depression Inventory-II (BDI-II) scale at the timepoints described in the Schedule of Activities of the Study Protocol. This is a 21 item self-reported scale, with each item rated by patients on a 4 point scale (ranging from 0-3.). The scale includes items capturing mood, (loss of pleasure, sadness, and irritability), suicidal ideation, and cognitive signs (punitive thoughts, self-criticism, self-dislike pessimism, poor concentration) as well as somatic signs (appetite, sleep, fatigue, libido).

Scores are obtained by adding up the total points from the series of answers. Higher total scores indicate more severe depressive symptoms. The standardized cutoffs are as follows:

- 0–13: minimal depression;
- 14–19: mild depression;
- 20–28: moderate depression;
- 29–63: severe depression.

The following descriptive statistics will be provided: n, arithmetic mean and SD. Frequencies and percentages will be displayed on items capturing mood, (loss of pleasure, sadness, irritability), suicidal ideation, and cognitive signs (punitive thoughts, self-criticism, self-dislike, pessimism, poor concentration) as well as somatic signs (appetite, sleep, fatigue, libido) on the BDI-II scale will be summarized.

- **Columbia Suicide Severity Rating Scale (C-SSRS)**

Frequencies and percentages will be displayed for patients with suicidal ideation, suicidal behavior, and self-injurious behavior without suicidal intent based on the C-SSRS during treatment.

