21. **Adverse Event (AE) Assessments:** AEs should be documented and recorded at each visit using the National Cancer Institute Common Terminology Criteria for Adverse Events (NCI CTCAE) version 4.03. The time period for actively eliciting and collecting AEs and Serious Adverse Events (SAEs) (“active collection period”) for each subject begins from the time the subject provides informed consent, which is obtained before the subject’s participation in the study (ie, before undergoing any study-related procedure and/or receiving investigational product), through and including a minimum of 28 calendar days after the last administration of the investigational product. During the active collection period, both non-serious AEs and SAEs are recorded on the case report form (CRF). If a subject begins a new anticancer therapy, the AE reporting period for non-serious AEs ends at the time the new treatment is started; however, SAEs must continue to be recorded on the CRF during the above-indicated active collection period.

22. Concomitant Medications and treatments: All concomitant medications and treatments will be recorded in the CRF from 28 days prior to enrollment and up to 28 days after the last dose of study treatment.
23. Mood Assessment: An assessment of mood via the Beck Depression Inventory II (BDI II) scale will be administered to subjects prior to the first day of lorlatinib dosing (ie, Cycle 1 Day 1) and then prior to dosing on Day 1 of Cycle 2 through –Cycle 6. After Cycle 6 Day 1, this test will be administered prior to dosing on Day 1 of every other cycle (ie, Cycle 8 Day 1, Cycle 10 Day 1, etc.) and at EOT.
24. Suicidal Ideation and Behavior: An assessment of suicidal ideation and behavior via the Columbia Suicide Severity Rating Scale (C-SSRS) will be administered to subjects prior to the first day of lorlatinib dosing (ie, Cycle 1 Day 1) and then prior to dosing on Day 1 of Cycle 2 through Cycle 6. After Cycle 6 Day 1, this test will be administered prior to dosing on Day 1 of every other cycle (ie, Cycle 8 Day 1, Cycle 10 Day 1, etc.) and at EOT.

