CNS effects could be categorized into 3 different categories including cognitive effects, mood effects and speech effects, which have been reported separately. The treatment related including cognitive effects, mood effects and speech effects have been observed in 21.7%, 15.3%, 8.1% patients in the 100-mg pooled group of Study 1001. The most common treatment related AEs in each category are memory impairment and irritability, slow speech, each occurring in 9.5%, 5.8% and 3.4% patients.

The CNS effects reported in both Phase 1 and Phase 2 portions have been generally considered mild (Grade 1 and Grade 2) in severity and transient, and improved upon dose delay and/or dose reduction. No Grade 4 or 5 CNS effects have been reported in the Phase 1 or Phase 2 portions. A more detailed evaluation of CNS effects is ongoing in the Phase 2 portion by routine assessment of cognition, mood, and suicidality through a computerized test (using laptops provided by Cogstate). Based on the preliminary results observed, the assessments in this Phase 2 study will be limited to mood and suicidality.

Changes in QTc and PR prolongation have also been observed in the study. QT interval prolongation was reported as treatment related AE in 5.4% patients in the 100-mg pooled group of Study 1001. And no Grade 3, Grade 4, Grade 5 treatment related AE have been reported. There were no atrioventricular block events in Phase 1, Grade 1 atrioventricular block was reported in 2 patients in Phase 2 as treatment related AE. No Grade 2 and above treatment related atrioventricular block have been reported. Basing on the preliminary evidence, the assessment of ECG and heart function will be conducted in this Phase 2 study.

In the 100-mg pooled group of Study 1001, 11.3% patients had a maximum decrease from baseline in LVEF $\geq 20\%$. The mechanism for the LVEF decreases is currently unclear, and it will need be further explored. Thus, the decrease of LVEF will also be evaluated in this study.

Peripheral neuropathy, mood disorders, cognitive disorders, speech disorders, vision disorders, diarrhoea, constipation, arthralgia, oedema, fatigue, weight increased are identified risks associated with lorlatinib administration, for which dose delay and/or dose reduction have been effective.

For complete details of the nonclinical/clinical studies, refer to lorlatinib current investigator's brochure

Efficacy

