3.4. Baseline Variables

Any deviations from the protocol specified window will be documented as protocol deviations. A separate definition of adequate baseline will be provided for tumor assessment related efficacy endpoints.

For efficacy analyses, safety (including Eastern Cooperative Oncology Group (ECOG) performance status) and baseline characteristics associated with tumor assessments (eg, number of sites of disease at baseline), the last assessment prior to first dose will serve as the baseline assessment.

Triplicate ECGs are collected; therefore the baseline for each ECG measurement is the average of the pre-dose measurements on the baseline day. Unscheduled assessments will not be included in the calculation of the average. Most of the ECG parameters will not be derived as they are provided by sites on the CRF. QTcF (Fridericia's correction) and QTcB (Bazett's correction) will be derived based on RR and QT. The average of the replicate measurements will be determined after the derivation of the individual parameters at each timepoint.

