3.5. Safety Endpoints

Safety endpoints will be summarized based on the on-treatment period unless otherwise specified.

On-treatment is defined as the time from the first dose of study treatment through the end of study follow-up (infinite lag) or start of new anti-cancer drug therapy, whichever occurs first. Adverse events occurring on the same day as the first dose of study treatment will be considered to have occurred during the on-treatment period. All other assessments which occur on the same day as the first dose of study treatment will be considered baseline assessments (see [Section 3.4](#) for the definition of baseline).

Safety data collected outside the on-treatment period as described above will be listed but not summarized.

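### SAP 6.5.9 plans no baseline-referenced summary of BDI-II or C-SSRS, so its scale tables cannot separate pre-existing from new or worsened symptoms

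*SAP*

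**What the plan says.** **Collection.** Protocol Schedule of Activities footnote 23 states that the "Beck Depression Inventory II (BDI II) scale will be administered to subjects prior to the first day of lorlatinib dosing". Footnote 24 says the same of the other scale: the "Columbia Suicide Severity Rating Scale (C-SSRS) will be administered to subjects prior to the first day of lorlatinib dosing". Both are repeated on Day 1 of Cycles 2 to 6, then on Day 1 of every other cycle, and at end of treatment. In the schedule grid neither scale is marked at screening, so the Cycle 1 Day 1 administration is the only scheduled pre-dose measurement.

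**Role.** CNS effects are among the secondary safety endpoints (Protocol section 2). Protocol 1.2.3.4, after describing the wider testing in the earlier study, says "the assessments in this Phase 2 study will be limited to mood and suicidality".

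**Baseline rules.** SAP 3.4 provides, for safety among other data, that "the last assessment prior to first dose will serve as the baseline assessment". SAP 3.5 adds: "All other assessments which occur on the same day as the first dose of study treatment will be considered baseline assessments". The same section makes the on-treatment period the default for safety summaries and sends safety data from outside that period to listings only.

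**Analysis.** For the BDI-II, SAP 6.5.9 describes the scale, lists four severity bands (0-13, 14-19, 20-28, 29-63) and then says "The following descriptive statistics will be provided: n, arithmetic mean and SD", plus item frequencies. For the C-SSRS it plans frequencies of suicidal ideation, suicidal behavior and "self-injurious behavior without suicidal intent based on the C-SSRS during treatment".

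**The concern.** Every patient in both cohorts receives lorlatinib, so no concurrent group shows what scores would have been without it. The natural way to read a repeated scale in that setting is against each patient's own pre-dose value. The protocol collects that value and the SAP defines it as a baseline, but the section that analyses the scales never uses it.

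A mean BDI-II on treatment then mixes symptoms that patients brought with them and symptoms that appeared or worsened on the drug. A C-SSRS count during treatment does not separate a patient who first reports ideation on treatment from one whose ideation was present before dosing and continued. What is at stake is whether the report's tables on these two instruments can answer the question for which the instruments were included.

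**Working it through.** The point rests on text and not on a design figure, so the check is mainly a cross-reading, followed by a short calculation of what the planned statistics can and cannot identify.

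1. **Does a baseline exist?** Yes. Footnotes 23 and 24 put both scales before dosing, and SAP 3.4 and 3.5 class those values as baseline.

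2. **Does any planned summary use it?** None was found.
   - SAP 6.5.9: no change from baseline, no shift, no new-onset category, and no statement of which time points are tabulated. The four bands feed no table.
   - SAP 3.5: pre-dose values fall outside the default summary period, and 6.5.9 makes no exception.
   - SAP 6.4.1 (baseline summaries): neither scale is listed.
   - Protocol 9.5: subsections on adverse events, laboratory tests, ECG and LVEF, with nothing on either scale.

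3. **How does the same SAP treat other repeated safety measures?**

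| Measure | SAP section | Baseline-referenced summary |
|---|---|---|
| Laboratory grades | 6.5.3 | Shift, baseline to worst post-baseline grade |
| Blood pressure, weight, pulse | 6.5.4 | Categories of increase and decrease |
| ECG | 6.5.5 | Shift tables; maximum increase from baseline |
| LVEF | 6.5.7 | Shift below normal; decrease of 20 points or more |
| ECOG | 6.5.8 | Shift, baseline to highest score |
| BDI-II, C-SSRS | 6.5.9 | None |

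4. **Scale check.** 21 items scored 0 to 3 give a maximum of 21 × 3 = 63, which agrees with the top band of 29-63. The listed bands can be used as they stand.

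5. **What could separate totals identify?** The documents give no scores, so the inputs here are assumptions. Let W be the number of patients at 14 or more at their worst on treatment, B the number at 14 or more at baseline, and O the number in both groups. New onset = W − O. With 100 patients and W = 20, O can lie anywhere from 0 to B for B up to 20, so new onset lies between 20 − B and 20:

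| B (assumed) | New onset |
|---|---|
| 0 | 20 |
| 5 | 15 to 20 |
| 10 | 10 to 20 |
| 20 | 0 to 20 |

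   A cross-tabulation of baseline by worst band gives O directly. SAP 6.5.9 plans neither W, nor B, nor the cross-tabulation.

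6. **And from means and SDs?** With the same SD at two times, SD of change = SD × √(2(1 − ρ)), where ρ is the within-patient correlation. With an assumed SD of 8 this gives 11.3 at ρ = 0, 8.0 at ρ = 0.5 and 3.6 at ρ = 0.9. The planned n, mean and SD do not give ρ, so the spread of individual change cannot be recovered from them.

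**The case against.** The best case on the other side has several parts, and much of it stands.

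- **These scales are not the only evidence on mood.** SAP 3.5.2 makes mood, speech and cognition events adverse events of special interest. SAP 6.5.1.1 analyses the treatment-emergent ones by time to onset, time to Grade 3 or 4 onset, and duration. A reader might infer that a drug effect on mood would go unseen, and the documents do not support that. What remains is that these are reported events and do not replace a summary of the two scales collected for the same purpose.
- **Nothing is lost.** Pre-dose and later values are collected for each patient. A reader might infer that old and new symptoms can never be told apart. That is true only of the planned tables.
- **Baseline suicidality should be uncommon.** Exclusion 16 (Protocol 4.2) names suicidal ideation or behavior that is active or within the past year. A report made only before dosing would also not enter a count restricted to treatment, so only persisting or recurring ideation is affected. This weakens the C-SSRS part. It does not remove it, because the exclusion rests on investigator or sponsor judgment and the C-SSRS is not scheduled at screening. No criterion limits the BDI-II score.
- **BDI-II might be tabulated by visit, with Cycle 1 Day 1 included.** SAP 6.5.9 refers to the scheduled time points when describing administration, but it does not say what is tabulated, and SAP 3.5 points the other way. Because a tabulated baseline mean cannot be assumed, the documents also do not support the claim that the planned table would show a false improvement. Even with that mean, patient-level change would be missing.
- **No dosing rule uses these scores.** Protocol Table 2 acts on toxicity grades, so the gap affects reporting and not treatment decisions.

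Two cautions on the evidence. Part of SAP 5.2.15 (continuous data) is blacked out, so its silence on change from baseline carries no weight here. The SAP change log says analysis was removed from 6.5.9 without saying what; a reader might infer that a baseline comparison was deleted, but the log does not show that.

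**Conclusion.** The point holds for the planned summaries. Followed as written, SAP 6.5.9 together with the defaults in SAP 3.5 yields BDI-II and C-SSRS tables that cannot distinguish pre-existing from new or worsened symptoms, although the pre-dose value is collected and the SAP references every other repeated safety measure in the comparison above to baseline.

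The size is modest. This is a descriptive secondary safety summary with no hypothesis or decision rule attached, and the primary endpoint is untouched. The effect is greater for BDI-II than for C-SSRS. How many patients would be affected cannot be stated, because the documents give no baseline or on-treatment scores; the ranges in the working depend on assumed counts. The conclusion also assumes that SAP 3.5 governs 6.5.9, which is the plain reading since 6.5.9 states no exception.

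**What to change.** Amend SAP 6.5.9 as follows:

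1. Name the last pre-dose BDI-II and C-SSRS values (scheduled on Cycle 1 Day 1) as baseline, and state that they are summarized, as an exception to the default in SAP 3.5.
2. Summarize BDI-II total score at baseline and at each scheduled visit, with paired change from baseline in patients who have both values and the number contributing at each visit.
3. Add a shift table of baseline band to worst on-treatment band, using the four cutoffs already listed.
4. Tabulate on-treatment C-SSRS ideation and behavior by whether it was present at baseline, giving new and pre-existing counts separately.

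The cost is SAP wording and a few extra tables by cohort and in total. No new visits, instruments or data are needed.

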7. INTERIM ANALYSES

No formal interim analysis will be conducted for this study. However, as this is an open-label study, the sponsor conduct unblinded reviews of the data during the course of the study for the purpose of safety assessment, facilitating pharmacokinetic/pharmacodynamic modeling, and/or to support clinical development.

8. CONSIDERATION ON COVID-19 IMPACT

During the study, COVID-19 emergency started and may have impacted study conduct. The following analysis will be conducted to assess the impact due to COVID-19.

Protocol deviations due to COVID-19 will be summarized.

A listing of patients impacted by COVID-19 will be provided.

If there are deaths due to COVID-19, sensitivity analysis for PFS and OS may be considered.

Appendix 1. Derived Objective Response per mRECIST v1.1 based on ICR Data

The primary endpoint is Objective Response (OR) in patients whose disease has progressed after crizotinib (Cohort 1) by independent central radiology (ICR) assessment per mRECIST v1.1 specified in protocol Appendix 3.

Per protocol Appendix 3, up to 5 CNS lesions were permitted to be identified as target lesion in addition to 5 extracranial lesions (up to 2 lesions per organ) at baseline. Furthermore, it was expected same set of brain lesions were used for both overall and intracranial assessment per RECIST v1.1 (Protocol Appendix 3).

However, per ICR (PAREXEL) operational procedure, overall assessment and intracranial assessment are performed independently for study B7461024; Overall assessment was based on RECIST 1.1 with up to 2 CNS lesions and 5 lesions in total were permitted to be identified as target lesion at baseline. While intracranial assessment was based on modified RECIST 1.1 that allows up to 5 measurable CNS lesions. Hence the brain lesions in the overall assessment and intracranial assessment may be different. And the overall assessment was conducted in a different way as specified in protocol Appendix 3.

To mitigate the potential risk due to the difference between ICR's procedure and that defined in protocol Appendix 3, programming derived overall assessment per modified RECIST v1.1 based on ICR tumor lesion data will be conducted to support the efficacy analysis.

Given the ICR data provided by PAREXEL, for each patient, the extracranial lesions identified in the overall assessment will be combined with the intracranial lesion identified in the intracranial assessment. The tumor response will then be derived based on tumor measurement/assessment per RECIST v1.1.

As there will be 2 radiologist to review each patient, for the derived response, only the readings from the reader agreed by the adjudicator will be used for the derivation. If there's no adjudication, which means that there's no discrepancy in the two readers' assessment for each time point, the reader with more representative extracranial lesion selected at baseline will be used for the derivation. The selection will follow the below rule:

- If both the extracranial assessment and intracranial assessment have adjudicators, the adjudicator's assessment will be applied, no matter whether the extracranial assessment and intracranial assessment have chosen the same reviewer's readings.
- If only the extracranial assessment or only intracranial assessment have adjudicator but not both of them, both of the extracranial assessment and intracranial assessment based on the exist adjudicator's decision will be applied.
- If no adjudicator appeared for both of extracranial and intracranial assessment, the selection will follow the below rule:
 - The one with more extracranial target lesion at baseline in overall assessment will be used if there was no adjudication;
 - If the two readers identified the same number of extracranial target lesion, the one with the larger SOD of extracranial target lesion will be chosen.
